2.1.3 Microbiome

2.1.3.1 Sample Types

There will be five types of samples collected for microbiome analysis, rectal, nasalpharangeal, nasal, conjutiva, and blood.

2.1.3.2 Sequencing and Pooling

Samples will be processed using either RNA-sequencing or 16S sequencing. In some instances, specimens will be pooled in the lab by combining aliquots of equal nucleic acid content by QuBit measurement of randomly selected individual's swabs into one microbiome sample per village. There will be one pooled sample of randomly selected specimens (e.g. 10 specimens) for each of the 30 villages, giving us 30 samples total for sequencing.

2.1.3.3 Time Points

Samples for a pre-morbidity study also know internally as "mini-microbiome", were collected in a separate indivdually randomized trial. The Morbidity study will provide microbiome samples collected at 12-months and 24-months.

2.1.3.4 Primary MicrobiomeAnalysis

Primary Analysis for rectal swabs collected pre-morbidity study, 16S-sequencing

Pre-Morbidity RCT (a.k.a. "mini-microbiome") will analyze 80 1-60 month old kids, randomized to placebo or azithromycin. We will obtain pre-treatment rectal swabs on day 0 and

post-treatment rectal swabs on day 5. We will compare diversity between arms at day 5, and between time points in each arm. Specific diversity measures to be examined are Shannon's Index (primary), Simpson's Index.

Primary Analysis for rectal swabs collected at 12-months, RNA-sequencing

Primary Analyses for the 12 month rectal swabs will conducted on pooled samples. We will use PERMANOVA on an **L2-norm** distance on bacterial **reads** to determine if treatment significantly explains the difference between the two groups.

Primary Analysis for rectal swabs collected at baseline and at 24 months, RNA and DNA sequencing; individual level analysis, not pooled. We propose to conduct PERMANOVA based on L2-norm; the outcome is the distance in centroid of the whole sequences, comparing the two treatment groups. Primary analysis is posttest only, but we will report comparisons at baseline as well.

PrimaryAnalysis for conjunctiva swabs, RNA-sequencing

Primary Analyses for the 24 month **conjunctiva swabs-RNA sequencing** will conducted on pooled samples. We will use PERMANOVA on an **L2-norm** distance on bacterial **reads** to determine if treatment significantly explains the difference between the two groups.

Primary analysis for rectal swabs at 36-months, DNA-sequencing

Primary analysis on the rectal swabs will be conducted on pooled samples. We will be using DESeq2 to determine if Campylobacter upsaliensis is upregulated in the placebo arm compared to the azithromycin arm. LEfSe will be used as a sensitivity test.

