2.1.3.5 Secondary MicrobiomeAnalysis

Secondary Analysis for all types and timepoints of microbiome samples will include:

- L1-norm distance PERMANOVA on bacterial reads
- For RNA-sequenced data: L1, L2-norm distances on virus, parasites, fungi.
- Simpson's and Shannon's estimated gamma diversities (transformed into effective number) will be compared by arm using a permutation test without correcting for baseline (ie post test only)
- Conjunctiva swabs, 16S-sequencing at 24-months will be conducted on individual samples. We will use PERMANOVA on an L1-norm distance on bacterial OTUs to determine if treatment significantly explains the difference between the two groups.
- TAC-card for rectal specimens of bacteria and viruses between two treatment groups at 24 months and at basline (PERMANOVA), and similarly for NP swabs (i.e., TAC-card)

Secondary analysis for rectal swabs at 36-months

We propose to compare the normalized abundance of MLS reads between treatment arms. Resistance to other classes of antibiotics will be compared. In addition, we will also assess for a difference in the normalized abundance of betalactams reads. P-values will NOT be corrected for multiple comparisons. Instead, we will estimate the FDR for resistance to each class of antibiotic.

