3.2 Morbidity Trial

Assuming approximately 12% baseline resistance (based on previous studies) and an ICC of approximately 0.051 (derived from the TEF study), we anticipate approximately 80% power to detect a difference of 18% (i.e., comparing 12% to 30%) assuming 80% carriage of pneumococcus and 10 specimens per community. For resistome comparisons, we anticipate approximately 80% power to detect a 16% difference (comparing 12% to 28%). We anticipate five such comparisons: (1) nasopharyngeal DNA, (2) nasopharyngeal RNA, (3) rectal DNA sequencing, (4) rectal RNA sequencing, and (5) rectal TAC-card.

4 Randomization

Simple random sampling will be used in each country. Within each country, a full list of eligible communities will be provided, and used to fill a column of a table. A second column will be populated with treatment arm names as follows. First, fifteen rows will be filled with the name **AzithroPlus**, and fifteen with the name **ControlPlus**. Then, one half of the remaining rows (rounding to even) will be filled with the name **Azithro**, and the remaining filled with the name **Control**. This column will be shuffled at random, yielding an assignment for each community.

Note that there is no stratification other than country, and the morbidity communities are randomized from the same pool as the mortality communities.

The randomization will be conducted using R. The function sample with option replace=FALSE will be used to conduct the random shuffling. Note that the choice of the random number seed completely determines the randomization. To ensure the integrity of the randomization, we will choose the seed as follows. We will use the units (least significant digit) of the daily high Fahrenheit temperature in eleven selected US cities on 15 July 2013 as reported by the National Weather Service. A confidential ordered list of these cities will be provided to the DSMC.

Masking will be strictly enforced. Each study site will provide one individual to whom the randomization list will be provided. Investigators and field teams must remain masked and must make no effort to determine which arm a community has been randomized to within the mortality trial or within the morbidity trial.

5 Abbreviations

ANCOVA Analysis of covariance

DSMC Data and Safety Monitoring Committee

HAZ height for age Z score

MUAC Mid upper arm circumference

SAP Statistical Analysis Plan

TF Trachomatous inflammation—follicular

TI Trachomatous inflammation-intense

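### In the 80-child pre-morbidity microbiome trial, the day-5 comparison of Shannon's Index is valid but, as written, leaves out the day-0 value already collected; day 0 enters only through within-arm comparisons that do not test the treatment effect

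*SAP*

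**What the plan says.** SAP 2.1.3.3 states that the pre-morbidity samples "were collected in a separate indivdually randomized trial". SAP 2.1.3.4 says that this trial "will analyze 80 1-60 month old kids, randomized to placebo or azithromycin". It continues "We will obtain pre-treatment rectal swabs on day 0 and" "post-treatment rectal swabs on day 5". The analysis is then given in one sentence: "We will compare diversity between arms at day 5, and between time points in each arm". On the outcome: "Specific diversity measures to be examined are Shannon's Index (primary), Simpson's Index".

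Both kinds of comparison stand under the primary analysis, unranked. No test is named, day-0 diversity is not mentioned as a covariate, and change is not compared between arms. No other section adds a baseline-adjusted diversity comparison for this trial. SAP 2.1.3.5, the secondary analysis for all microbiome sample types and time points, says of the estimated gamma diversities that they "will be compared by arm using a permutation test without correcting for baseline (ie post test only".

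Elsewhere the SAP does use baseline. The morbidity outcomes in 2.1.2 are modelled with baseline values as covariates, and the clinic case counts in 2.1.3.6 are adjusted for the preceding year's count.

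**The concern.** Shannon's Index in the same child five days earlier is a natural prognostic covariate for the day-5 value, and the design already pays for it. If it is left out, the randomised comparison is less precise than the data allow, and in a trial of 80 children that can matter.

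The plan instead uses day 0 to compare time points separately in each arm. Each such comparison mixes any drug effect with anything else that changes over five days. A significant change in one arm and a non-significant change in the other is not evidence that the arms differ. Because these comparisons are listed beside the randomised one without a rank or a descriptive label, a report could present them as if they were.

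**Working it through.** **Inputs from the documents.** 80 children; individual randomisation, so no cluster design effect; one swab at day 0 and one at day 5; Shannon's Index primary. The SAP gives no power, SD, target difference, alpha, allocation ratio or day 0 to day 5 correlation for this trial, so there is no planned figure to reproduce.

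**Assumptions.** 40 per arm, two-sided alpha 0.05, true difference d = 0.5 SD, and correlation r shown at 0, 0.3, 0.5 and 0.7.

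**Step 1: precision.** Adjusting for day 0 multiplies the outcome variance by 1 − r². The standardised difference becomes 0.5/√(1 − r²), the noncentrality is that value × √(40/2), and power comes from the noncentral t distribution with 78 degrees of freedom. The number of children that would give the same precision at day 5 alone is 80/(1 − r²).

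| r | 1 − r² | Standardised difference | Noncentrality | Power | Equivalent children |
|---|---|---|---|---|---|
| 0 (day 5 only) | 1.00 | 0.500 | 2.24 | 59.8% | 80 |
| 0.3 | 0.91 | 0.524 | 2.34 | 63.9% | 88 |
| 0.5 | 0.75 | 0.577 | 2.58 | 72.2% | 107 |
| 0.7 | 0.51 | 0.700 | 3.13 | 87.1% | 157 |

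Estimating the slope costs little. Dividing the standardised difference by √(1 + 1/76) and using 77 degrees of freedom gives 63.3%, 71.7% and 86.7% for the last three rows. The detectable difference at 80% power (normal approximation) is (1.960 + 0.842) × √(2/40) = 0.626 SD at day 5 alone. Multiplying by √(1 − r²) gives 0.598, 0.543 and 0.447 SD.

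**Step 2: within-arm comparisons when the drug does nothing.** Let both arms share the same true change, and let p be the power of a paired t-test on 40 children. The arms are independent, so exactly one is significant with probability 2p(1 − p).

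| Shared change, in SDs of change | p | 2p(1 − p) |
|---|---|---|
| 0 | 0.050 | 9.5% |
| 0.1 | 0.095 | 17% |
| 0.2 | 0.235 | 36% |
| 0.31 | 0.481 | 50% |
| 0.4 | 0.694 | 42% |
| 0.6 | 0.959 | 8% |

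The maximum is 50%, reached when p = 0.5. Simulation of 20,000 trials per setting, with drift measured in SDs of the outcome and r from 0.3 to 0.7, gave 9.1–9.2% with no drift and 20–50% with a drift of 0.2 to 0.4 SD. In the same simulations the day-5 t-test between arms rejected in 4.8–5.3% of trials, so its type I error is sound.

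**The case against.** The strongest reply is that nothing is wrong with the randomised comparison. It is unbiased, it keeps its error rate, and it stands in the plan alongside the within-arm comparisons. That is correct: the point concerns efficiency and presentation.

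A second reply is that the SAP names no test, so an arm comparison at day 5 could still carry a day-0 covariate. That is possible. The explicit post-test-only wording in 2.1.3.5 concerns secondary gamma diversities and does not govern this comparison. But the only stated use of day 0 is within arm, and no section states an adjusted comparison, so the text at least needs to settle the matter.

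Several stronger readings are tempting but not supported:

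- A reader might infer that the trial will claim efficacy from one arm changing and the other not. The SAP nowhere says so.
- A reader might take a false contrast of 36–50% as the expected risk. That range comes from choosing a shared drift of 0.2 to 0.4 SDs of change. The documents give no drift, and the same formula gives 9.5% at zero and 8% at 0.6.
- A reader might see the entry "ANCOVA Analysis of covariance" in SAP Section 5 as a sign of a planned analysis that was lost. TF and TI are listed there too without being used in any analysis, so the entry shows nothing.
- A reader might extend the point to village diversity at 24 months. In SAP 2.1.3.4, post-test-only is a stated choice for the 24-month primary analysis, with baseline comparisons also reported, and the village-level correlation over two years is unknown. The calculation above does not carry over.

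Finally, this is a side study. Protocol 1.2 makes microbial diversity an ancillary, non-core aim, and no mortality or resistance conclusion depends on it.

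**Conclusion.** The point holds as a low-cost improvement. The planned day-5 comparison is valid but, as written, discards a covariate that the trial collects, and the within-arm comparisons do not fill that gap. The size depends on the day 0 to day 5 correlation. For a 0.5 SD difference with 40 per arm, the gain in power is about 4, 12 or 27 percentage points at r of 0.3, 0.5 or 0.7, and about nil near zero. The risk that exactly one arm looks significant under an inert drug is about 9% without drift and at most 50% with a shared one. Correlation, drift, allocation ratio and target difference are all assumptions. The principle is firm; the magnitude is not.

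**What to change.** In SAP 2.1.3.4, name one primary test for this trial: the arm effect on day-5 Shannon's Index, adjusted for the same child's day-0 Shannon's Index (ANCOVA), with a permutation P-value obtained by reshuffling children between arms. Keep Shannon's Index on the scale already stated. State how a child without a usable day-0 swab is kept in the analysis, for example with a missing-value indicator. Present the within-arm changes as description, with estimates and intervals but no P-values.

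The cost is a few sentences of SAP text and no new data. The SAP describes these samples as already collected, so date the change in the revision history. If the data have already been analysed, report the planned day-5 comparison as it stands and add the adjusted result, labelled as a later addition.

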1.2 Morbidity Trial

The trial profile is given in the Manual of Operations. In the morbidity trials, communities are randomized to two arms: **AzithroPlus**, or **ControlPlus**. At each study site, 15 communities each are randomized to **AzithroPlus** and to **ControlPlus**. The trial is a placebo controlled, double masked, community randomized, multicenter clinical trial. The profile is given in the Manual of Operations, Ch. 3.

2 Statistical Analysis

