2.1.2 Morbidity Trials

Primary Analyses (Morbidity Study).

The morbidity analyses are to be conducted on a country-specific basis. Each outcome will be addressed in a separate analysis. Outcomes are taken at 0, 12, and 24 months.

The outcome and analysis plan for all non-core studies must be submitted to the Steering Committee for approval.

The outcomes for this study are listed on www.clinicaltrials.gov. Analyses may be conducted at the village level (accounting thus for clustering), or, when possible, at the individual level accounting for clustering by using mixed effects regression. The listed primary outcomes (4 February 2015) are:

- 1. Height over time in children aged 1-60 months (Niger & Malawi)
- 2. Weight, corrected for height over time in children aged 1-60 months (Niger & Malawi)
- 3. Fraction of macrolide resistance in nasopharyngeal swabs in children 1-60 months (core). Note that for Niger, this is phenotypic, and is a binary outcome at the individual level.
- 4. Fraction of macrolide resistance from stool specimens in children 1-60 months (core). For Niger, this includes RNA, DNA, and TAC-card methods (a binary outcome at the individual level).
- 5. Fraction of macrolide resistance by nasal swabs in children 1-60 months (Niger only). For Niger, this is based on RNA and DNA sequencing (a binary outcome at the individual level).
- 6. Presence of malaria parasites in children 1-60 months (core activity)
- 7. Fraction of conjunctival swabs yielding ocular chlamydia in children 1-60 months (Niger)

Nonnormality, heteroskedasticity, clustering, and outliers will be assessed appropriately.

Secondary Analyses (Morbiditiy Study).

Common templates will be used. Analysis will use cluster-level variables for malaria parasites, macrolide resistance in NP swabs, macrolide resistance in nasal swabs, macrolide resistance in stool specimens, and ocular chlamydia. Clustered logistic regression using baseline values will be used, with the outcome being the 12 and 24 month observations, and time and treatment as covariates in addition to baseline values. Permutation P-values will be reported.

Model checking will be performed to identify poorly fitting models, using the residuals versus fitted values plot and by finding high leverage points. Significance testing will be conducted using permutation tests.

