The analysis will follow these guiding principles: (1) All data from all available participants will be included, regardless of whether the patient contributed data to all time periods, or to only a subset of periods; (2) The analysis must reflect the longitudinal nature of the followup and the clustered nature of the design, (3) Permutation testing will be used to compute the P-value, (4) The model must be fully prespecified prior to any analysis of any kind.

If a village randomized to the morbidity study has fewer than 40 children upon census, an additional morbidity village may be recruited in its place.

All secondary analyses are identified as the following:

- 1. Repeated measures of outcomes for children present at baseline and possibly followed for 24 months. using 0, 12, and 24-month measurements (or all time points processed).
- 2. Analyze additional outcomes: WHO z-values (height for age, weight for height, weight for age) and MUAC. P-value will be adjusted for these additional outcomes.
- 3. Separate outcome using cross-sectional post-test children 25 months and under using 0.05 alpha. Analysis will be similar to longitudinal (height for age, weight for height, outliers, etc. Note that these children were not eligible for the primary analysis.
- 4. Community-level varaiables will be considered from CSI records.
- 5. Per-protocol analysis will be performed by arm, i.e. only including those who took the treatment.
- 6. Other outcomes by treatment arm at 24 months will include percent wasted and percent stunted. Permutation p-values will be computed here.

Sensitivity analysis including the outliers as well as dissociating the measurements in a repeated measures analysis will be conducted. Appropriate consideration will be analyzed for transfromation, heteroskedacity, and outliers. Additional prespecified secondary analyses are listed on www.clinicaltrials.gov.

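### The 36-month primary rectal analysis names DESeq2 without stating a permutation P-value; if the package default is used on about 15 v 15 village pools, its 5% error rate is not assured

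*SAP*

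**What the plan says.** The 36-month paragraph of SAP 2.1.3.4 has three elements. The unit is the pool: "Primary analysis on the rectal swabs will be conducted on pooled samples". The method is DESeq2 for one named species: "We will be using DESeq2 to determine if Campylobacter upsaliensis is upregulated in the placebo arm compared to the azithromycin arm". The fallback is a second method: "LEfSe will be used as a sensitivity test". The paragraph gives no source for the P-value, no alpha, no sidedness and no number of pools.

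Other parts of the plan bear on it:

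- SAP 2.1.3.2, on pooling: "There will be one pooled sample of randomly selected specimens (e.g. 10 specimens) for each of the 30 villages". SAP 1.2, on allocation: "At each study site, 15 communities each are randomized to" each morbidity arm.
- SAP 2.1.2, on the morbidity study: "Significance testing will be conducted using permutation tests", repeated among the guiding principles as "3) Permutation testing will be used to compute the P-value".
- SAP 2.1.3.4, on the other cluster-trial microbiome primaries (rectal at 12 months, rectal at baseline and 24 months, conjunctiva at 24 months): all use PERMANOVA, which is a permutation test.
- The contingency-study SAP for Niger years 3-4, which include month 36: morbidity communities are analysed on the Stage 1 template, and primary analyses are two-sided at 0.05. Its statistical considerations set 10,000 replications for permutation tests.

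**The concern.** DESeq2 fits a negative binomial model to counts and by default reports a Wald P-value that relies on large samples and on that model. Here there would be about 15 observations per arm. Each is a pool of roughly ten children, so its count is the sum of the loads of a few carriers. Such sums can be heavy-tailed, or zero in many pools, and nothing guarantees a negative binomial shape.

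This one P-value decides a declared primary result. If the test is anticonservative, a chance concentration of heavy shedders in one arm is reported as a drug effect. If it is conservative, power is lost. The plan avoids this risk in its other cluster-trial microbiome primaries by using permutation, and it gives no reason for a different approach at month 36.

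**Working it through.** **1. Number of pools.** SAP 1.2 gives 15 communities per arm per site, and SAP 2.1.3.2 gives one pool per village, "for each of the 30 villages, giving us 30 samples total for sequencing". So 15 + 15 = 30, which reproduces the plan's figure. Applying it to month 36 is an inference. The 36-month paragraph gives no count, 2.1.3.2 says pooling happens in some instances with ten specimens as an example, and 2.1.3.3 lists only 12 and 24 months. The plan states no power or error rate for the DESeq2 analysis, so there is no further figure to reproduce.

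**2. Default DESeq2 with no arm effect.** Version 1.42.0 was run with its default Wald test and outlier handling, poscounts size factors and independent filtering off. There were 15 v 15 samples, library-size variation (log SD 0.4), 150 background taxa and 630 null taxa per setting. The Monte Carlo standard error is √(0.05 × 0.95 / 630) = 0.9 points at 5%, and √(0.256 × 0.744 / 630) = 1.7 points at 25.6%, treating taxa as independent. Means, dispersions and zero fractions are assumptions. The last two columns are rejection rates at two-sided 0.05.

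| Mean, dispersion, added zero fraction | Pools at zero | DESeq2 | Wilcoxon, same data |
|---|---|---|---|
| 100, 1, 0 | 1% | 7.6% | 4.6% |
| 100, 2, 0 | 7% | 7.1% | 5.1% |
| 10, 5, 0 | 46% | 11.6% | 5.4% |
| 5, 10, 0 | 67% | 9.5% | 5.9% |
| 100, 1, 0.5 | 50% | 0.8% | 4.4% |
| 100, 2, 0.7 | 71% | 14.3% | 4.8% |
| 20, 2, 0.7 | 73% | 13.7% | 5.4% |
| 100, 2, 0.85 | 85% | 25.6% | 5.2% |

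In the last setting, 17% of null taxa had P < 0.001.

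**3. A different data model, same package.** Pools were built from ten children with village ICC 0.05, assumed carriage of 15-30% and lognormal abundance. DESeq2 gave 1.5% and 5.2% (log-abundance SD 1), 4.5% and 9.7% (SD 1.5), and 14.7% (30% carriage, SD 2). With beta-binomial carriage, the chance that a pool has no carrier is the product over i = 0 to 9 of (19(1−p) + i)/(19 + i), where 19 = (1 − 0.05)/0.05. That is about 6% at p = 0.30 and 27% at p = 0.15. The 14.7% therefore arose with the organism in about 94% of pools, so heavy tails alone can move the rate. Taxa that truly were negative binomial gave 5.2-5.7% here, against 7.1-11.6% in the first four rows above. The size of the error clearly depends on the assumed inputs.

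**4. Permuting village labels.** A permutation test on the mean log count (999 permutations, 2,000 null runs per setting, standard error √(0.05 × 0.95 / 2000) = 0.5 points) rejected in 3.6% to 5.5% of runs in 11 of 12 settings. It rejected in 1.6% with 85% of pools at zero. Permuting the log fold change of arm means on carriage-based null data gave 4.7-5.5% in six settings, where a hand-coded negative binomial Wald test (not DESeq2) gave 2.1-19.3%. A further check of the same kind gave 4.4-6.5%, against 4.3-18.2% for the Wald test. Permuting the full DESeq2 statistic was not run. It would hold at most 5% by construction, because the labels were assigned by random shuffling.

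**5. Why 85% zeros is the extreme case.** On average 30 × 0.15 = 4.5 pools are positive. With four positive pools all in one arm, the smallest possible two-sided permutation P is 2 × (15·14·13·12)/(30·29·28·27) = 0.0996. With five it is 2 × (15·14·13·12·11)/(30·29·28·27·26) = 0.042. Data that thin cannot support P < 0.001, yet the default test returned such values for 17% of null taxa.

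**The case against.** The best defence is that the text does not contain the error. Four stronger readings are tempting, and the documents support none of them as a flat claim.

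- **The organism is sparse.** Nothing in the documents gives its carriage or abundance. Every error rate above describes assumed inputs, and the spread between data models shows it.
- **The P-value comes from the DESeq2 model.** The paragraph is silent. The mortality primary in SAP 2.1.1 pairs negative binomial regression with a permutation P-value, so naming a count model does not settle the matter.
- **The SAP breaks its own rule.** The permutation statements are in 2.1.2, under the secondary morbidity analyses, and 2.1.3 does not repeat them. Section 2.1.3 is not uniformly permutation-based either: clinic case finding (2.1.3.6) uses Poisson regression with no permutation. The revision history describes the microbiome work as part of Morbidity, and the contingency SAP carries the Stage 1 template forward. Both suggest the rule applies, but that is a reading.
- **Sidedness is undefined.** The hypothesis is worded in one direction, but the contingency SAP sets morbidity primaries in years 3-4 as two-sided at 0.05.

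It can also be said that LEfSe screens with a rank test and might expose a result driven by a few pools, and that the microbiome is a non-core ancillary aim.

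These points limit the wording but leave the gap. SAP 2.1.1 spells out its permutation test, and 2.1.3.4 does not. An analyst following the 36-month paragraph literally would report the package default. A sensitivity analysis may disagree with that P-value but does not correct it. If permutation was always intended, the paragraph should say so.

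**Conclusion.** The point holds in a limited form. A declared primary analysis names DESeq2 and omits the source of its P-value, in a plan whose other cluster-trial microbiome primaries use permutation. If the default is used on about 15 v 15 pools, the false-positive rate at nominal 5% could be anywhere from about 1% to 26% under the distributions tried, and about 7% with few zeros. Label permutation held about 4% to 6%, or was conservative at 1.6% in the sparsest setting.

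This rests on three assumptions: that the default P-value would be used, that there are about 30 village pools at month 36, and that the simulated distributions bracket the real one. The range does not estimate this trial's actual error rate or its direction. Clustering is not the problem, since each village contributes one pool. The mortality result is unaffected.

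**What to change.** Add to the 36-month paragraph of SAP 2.1.3.4 that:

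- the estimate is the DESeq2-normalised log fold change between arms;
- the primary P-value comes from permuting the arm labels of the village pools with 10,000 permutations, two-sided at 0.05, as the contingency SAP already sets for permutation tests and morbidity primaries;
- the model-based DESeq2 P-value and LEfSe are supportive.

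The same edit should state the number of pools per arm at month 36 and how the fold change is defined if one arm has no reads of the organism.

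No new data are needed. Size factors do not use the arm labels, so normalisation is done once and permuting the fold change takes minutes. The cost is that the P-value may be slightly less favourable, and that the test will be conservative if very few pools contain the organism.
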